9.3.5.3 Pharmacokinetic Analyses

Pharmacokinetic analysis will be the responsibility of the Clinical Pharmacology Modeling & Simulation (CPMS) department within Novartis. Plasma dabrafenib and metabolites including hydroxy-, desmethyl-, and carboxy-dabrafenib and trametinib concentration-time data will be analyzed by standard noncompartmental methods in subjects from whom the full PK blood sample scheme were collected. Calculations will be based on the actual sampling times recorded during the study. From the plasma concentration-time data, the following pharmacokinetic parameters will be determined for dabrafenib and metabolites and trametinib, as data permit:

Steady-state (all subjects) - trough concentration at steady-state (C_{trough}), C_{max} , t_{max} , $AUC(0-t)$, $AUC(0-8)$, ($AUC(0-12)$; dabrafenib and metabolites only), $AUC(0-24)$ (trametinib only), and apparent terminal phase half-life ($t_{1/2}$) for trametinib and dabrafenib and metabolites. The metabolite to parent ratio for $AUC(0-12)$ will be calculated for each metabolite of dabrafenib. $AUC(0-12)$ on Day 15 will be estimated for dabrafenib and metabolites by setting the plasma concentration 12 hours after dosing equal to the predose concentration. The $AUC(0-24)$ on Day 15 will be estimated for trametinib by setting the plasma concentration 24 hours after dosing equal to the predose concentration.

[REDACTED]

Noncompartmental pharmacokinetic parameters will be listed and summarized by day. Separate summaries will be created for parameters calculated with the dense blood sampling scheme and the sparse blood sampling scheme. No formal statistical analysis of the pharmacokinetic parameters is planned.

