Trametinib, dabrafenib and dabrafenib metabolites C_{max} , t_{max} , C_{trough} , $AUC(0-t)$, and $AUC(0-8)$; $AUC(0-12)$ (dabrafenib and dabrafenib metabolites only), $AUC(0-24)$ (trametinib only) and the dabrafenib metabolite to dabrafenib ratio of $AUC(0-12)$. For Chinese patients, the accumulation ratio will be calculated by using the pharmacokinetic parameters from Day 1 and Day 15. Population PK parameters will include: apparent clearance following oral dosing (CL/F), volume of distribution (V/F), and absorption rate constant (K_a) for dabrafenib and trametinib.

[figure not shown]

1 Introduction

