The risk-to-benefit ratio in this patient population remains favorable.

[figure not shown]
2 OBJECTIVE(S) and endpoints

Table 1 lists the study objectives and corresponding endpoints.

Table 1 Study Objectives and Endpoints

Objectives	Endpoints
Primary	

 To determine the objective response rate (ORR) of dabrafenib in combination with trametinib in subjects with BRAF V600 mutation-positive, unresectable or metastatic acral lentiginous or cutaneous melanoma 	
 ORR defined as the percentage of subjects with evidence of a confirmed complete response (CR) or partial response (PR) as per RECIST v1.1 [Eisenhauer EA 2009].
Secondary	

 To further evaluate the antitumor activity (progression-free survival (PFS), duration of response, and overall survival (OS)) 	
 Duration of response is defined as the time from first documented evidence of CR or PR until the earliest date of documented radiological progression or death due to any cause among subjects who achieved a confirmed CR or PR. PFS defined as the time from first dose of study treatment until the first date of either objective disease progression or death due to any cause. OS defined as the interval from first dose of study treatment to the date of death, irrespective of the cause of death; subjects still alive will be censored at the date of the last contact.

 To assess exposures to dabrafenib, dabrafenib metabolites, and trametinib after a single dose (Chinese patients) and at steady- 	
 Trametinib, dabrafenib and dabrafenib metabolites concentrations by visit. Noncompartmental PK parameters include

Objectives	Endpoints
state, and characterize the population pharmacokinetics and pharmacodynamics of dabrafenib and trametinib	trametinib, dabrafenib and dabrafenib metabolites C _{max} , t _{max} , C _{trough} , AUC(0-t), and AUC(0-8); AUC(0-12) (dabrafenib and dabrafenib metabolites only), AUC (0-24) (trametinib only) and the dabrafenib metabolite to dabrafenib ratio of AUC(0-12). For Chinese patients, the accumulation ratio will be calculated by using the pharmacokinetic parameters from Day 1 and Day 15. Population PK parameters include, apparent clearance following oral dosing (CL/F), volume of distribution (V/F), and absorption rate constant (K _a) for dabrafenib and trametinib.

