17. A 4-week supply of study medication should be dispensed at each scheduled study visit as of Day 1; Dosing instructions must be provided. Subjects should start treatment as soon as possible after enrolment but no later than 72 hours post-enrolment.
18. Subjects should be instructed to return study drug at each visit; compliance will be assessed by querying the subject and counting tablets/capsules. Dose modifications and interruptions must be recorded.
19. Analysis of clinical chemistry and hematology samples will be performed by a central laboratory
20. Serum pregnancy test is required at Screening. Subsequent tests may be urine tests, and should be performed as clinically indicated.
21. Blood samples for PK analysis will be drawn on Day 15 at predose (within 30 minutes prior to dosing) and 1, 2, 4, 6, and 8 hours after dosing. For subjects in China, PK blood samples will be drawn on Day 1 at predose (within 30 minutes prior to dosing) and 0.5, 1, 1.5, 2, 3, 4, 6, 8, 10 and 24 (pre dose on Day 2) hours and on Day 15 at predose (within 30 minutes prior to dosing) and 0.5, 1, 1.5, 2, 3, 4, 6, 8, 10 and 24 (pre dose on Day 16) hours after dosing. Refer to section 7.5 and 5.9.1.1 for details on pharmacokinetics blood sampling including liver PK sampling.
22. [REDACTED]

- 
25. Follow-up contact will include clinic visits, telephone contacts, and e-mail communications. The date of contact must be recorded. After treatment discontinuation, subjects should be contacted for follow-up every 12 weeks \pm 7 days until death.
 26. After treatment discontinuation, any new anti-cancer therapy initiated will be recorded until study completion/withdrawal/lost to follow-up, or death.
 27. The treatment discontinuation visit should be performed within 30 days of the subject's last dose. If a subject discontinues study treatment at a scheduled visit, the assessments performed at that visit can be used to fulfil the treatment discontinuation visit requirements. Laboratory assessments and other required assessments do not need to be repeated at the discontinuation visit if they were performed within 14 and 30 days, respectively, of the discontinuation visit. If the last disease assessment was >8 weeks prior to study withdrawal and disease progression had not been documented, a disease assessment should be obtained.

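### The Day 15 trametinib AUC(0-24) rule puts the predose value in place of the 24-hour concentration for all subjects, although a measured 24-hour sample is scheduled for subjects in China

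*Protocol*

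**What the plan says.** **The rule.** Protocol 9.3.5.3 opens its list of Day 15 parameters with "Steady-state (all subjects) - trough concentration at steady-state". In that paragraph, AUC(0-24) is estimated "for trametinib by setting the plasma concentration 24 hours after dosing equal to the predose concentration". The readable text makes no exception for country or sampling scheme.

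**The samples.** Table 20 footnote 21 sets two Day 15 schedules:
- General (sparse) scheme: predose "and 1, 2, 4, 6, and 8 hours after dosing".
- China (dense) scheme: predose, then ten post-dose times that end "6, 8, 10 and 24 (pre dose on Day 16) hours after dosing". Day 1 has the same times, with its last sample taken before the Day 2 dose.

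**Related text.**
- Section 9.3.5.3 restricts noncompartmental analysis to subjects with the full sampling scheme, uses actual sampling times, and summarises dense and sparse results separately.
- The abbreviation list defines AUC(0-t) as running to the last quantifiable concentration.
- Protocol Table 1 says that, for Chinese patients, "the accumulation ratio will be calculated by using the pharmacokinetic parameters from Day 1 and Day 15". It does not name the parameter.
- SAP Table 1-1 lists trametinib AUC(0-24) among the noncompartmental parameters for Mainland Chinese subjects.
- SAP 2.9 makes PK not applicable to the final analysis because it was reported earlier.

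**The concern.** The substitution fills a gap that exists only in the sparse scheme. A Chinese subject who qualifies for noncompartmental analysis by having the full scheme has a measured 24-hour value, and the rule overrides it. The SAP ties these parameters to Mainland Chinese subjects, so the substitution would fall on the group that does not need it.

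Two things follow. First, AUC(0-24) takes its end point from predose, while AUC(0-t) takes the measured one when it is quantifiable. One subject can then have two different areas over the same 24 hours with no stated reason. Second, the substitution is exact only if predose and 24-hour concentrations are equal. That can fail if trametinib is still accumulating or if doses just before Day 15 were missed or mistimed. The Day 15 visit has a window of 3 days either side, and assessments stay on the calendar when treatment is delayed, so profiles can be drawn soon after an interruption.

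The dabrafenib AUC(0-12) rule is different: neither scheme has a 12-hour sample, so a substitution is needed there.

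**Working it through.** The plan gives no figure of its own on this point, so there is nothing to reproduce. The check is how far AUC(0-24) moves when predose replaces the true 24-hour value.

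**Inputs from the documents.** Dense Day 15 times: 0, 0.5, 1, 1.5, 2, 3, 4, 6, 8, 10 and 24 h. Trametinib is given once daily.

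**Assumptions.** The documents give no half-life; the range taken is 24-240 h. The model is one-compartment oral with linear kinetics, ka = 1/h and linear trapezoids.

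**1. Weight of the last sample.** In the 10-24 h trapezoid, C24 has weight (24 − 10)/2 = 7 h.

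**2. Error formula.** Let predose be lower than the true C24 by a fraction d, and let r be the average concentration divided by C24.
- Change in AUC = 7 × d × C24
- AUC(0-24) = 24 × r × C24
- Relative error = 7d/(24r)

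For d = 10%: 0.7/(24 × 1.5) = 1.9% and 0.7/(24 × 1.2) = 2.4% (r assumed 1.2-1.5).

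**3. Missed Day 14 dose, half-life 24 h.** Let T be the usual steady-state trough. Each dose contributes s to the concentration 24 h later, and T = 0.5T + s, so s = 0.5T.
- Predose on Day 15 = 0.5T
- True C24 = 0.5 × 0.5T + 0.5T = 0.75T
- d = 1 − 0.5/0.75 = 33%
- Error = 7 × 0.333/(24 × 1.5) = 6.5% to 7 × 0.333/(24 × 1.2) = 8.1%

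**4. Full model on the dense times.** Underestimate of AUC(0-24) from the substitution:

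| Assumed half-life | Full dosing | Day 14 missed | Days 12-14 missed |
|---|---|---|---|
| 24 h | 0.0% | 7.0% | 16.5% |
| 48 h | 0.1% | 2.8% | 8.9% |
| 96 h | 0.4% | 1.3% | 3.6% |
| 120 h | 0.6% | 1.3% | 3.0% |
| 240 h | 1.1% | 1.5% | 2.3% |

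With full dosing, predose/C24 on Day 15 is 0.961-1.000 over this range. If the visit falls on Day 12, d is at most 5.5% and the AUC error at most 1.6%.

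**5. Late dose.** Suppose the Day 14 dose is 6 h late and the half-life is 24 h.
- Its residue at predose is 0.5T × 2^(6/24) = 0.595T, so predose = 0.5T + 0.595T = 1.095T
- True C24 = 0.5 × 1.095T + 0.5T = 1.047T
- Predose is 4.5% above C24, and AUC(0-24) is overstated by 7 × 0.045/(24r) = 0.9-1.1% for r = 1.5-1.2

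A late dose can therefore reverse the sign.

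**The case against.** **A gap-filling rule.** Section 9.3.5.3 speaks of standard methods, actual sampling times and parameters as data permit. An analyst could take the substitution to apply only where no 24-hour value exists. That is a sensible reading, but the paragraph covers all subjects and the readable text does not state the limit.

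**Redaction and an unseen SAP.** A blacked-out block follows the rule in 9.3.5.3, and PK was reported under an earlier SAP that is not among the documents. Either could define the dense-scheme analysis. This stands: whether the literal rule was applied is unknown.

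**The accumulation ratio.** A reader might infer that the ratio compares a measured Day 1 end point with an imputed Day 15 one. The documents do not support that. The protocol and SAP refer only to pharmacokinetic parameters. Cmax would not use the substitution, and AUC(0-t) to 24 h would use the measured sample.

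**Steady state assumed rather than measured.** This too might be inferred, and it goes too far. Both the predose and the 24-hour samples are collected and can be compared. The fault is confined to AUC(0-24).

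**Little turns on it.** PK is a secondary, descriptive objective with no formal analysis planned. After missed doses the Day 15 profile is disturbed even when C24 is measured, so the change does not restore a valid steady-state ratio. Both points are fair and limit the importance of the finding.

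**Conclusion.** The rule and the sampling schedule do not fit together for subjects in China. As written, Day 15 trametinib AUC(0-24) in the dense scheme replaces a scheduled measurement with an assumed value and can disagree with AUC(0-t).

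The likely effect is minor: at most about 1% with full dosing on Day 15 and about 1-7% after a missed Day 14 dose (6.5-8.1% by the simple formula at a 24 h half-life). It reaches 2-16% after three missed doses. These sizes rest on assumed half-lives of 24-240 h, an assumed absorption rate, linear kinetics and linear trapezoids.

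One might put d at 50% for a missed Day 14 dose at a 24 h half-life and so expect a larger error. That measures predose against the usual trough instead of the true 24-hour value, which is itself lower. The right d is 33%.

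No effect on the accumulation ratio is established. The ratio would carry the same percentage error only if it is based on AUC(0-24).

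**What to change.** In Protocol 9.3.5.3, state that Day 15 trametinib AUC(0-24) uses the observed 24-hour concentration at its actual sampling time wherever it was obtained. The 24-hour value is set equal to predose only for the sparse scheme or when the 24-hour sample is missing.

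Because PK has already been reported, the sponsor should confirm which value that analysis used. If it was the measured value, a clarifying sentence in the final report is enough. If it was predose, re-run AUC(0-24) for the dense-scheme subjects and any ratio based on it. If the report does not already name the parameter behind the accumulation ratio, it should do so.

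The cost is one sentence and, at most, one parameter and its dependent ratio recalculated. No new samples are needed. An optional extra is to tabulate C24/predose in the dense-scheme subjects, which uses existing data to check the substitution that the sparse scheme still relies on.

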9.3.5.4 Pharmacokinetic/Pharmacodynamic Analysis

[REDACTED]

10 Study CONDUCT CONSIDERATIONS

10.1 Posting of Information on Publicly Available Clinical Trial Registers

Study information from this protocol will be posted on publicly available clinical trial registers before enrolment of subjects begins.

10.2 Regulatory and Ethical Considerations, Including the Informed Consent Process

Prior to initiation of a study site, Novartis will obtain favourable opinion/approval from the appropriate regulatory agency to conduct the study in accordance with ICH Good Clinical Practice (GCP) and applicable country-specific regulatory requirements.

The study will be conducted in accordance with all applicable regulatory requirements.

The study will be conducted in accordance with ICH GCP, all applicable subject privacy requirements, and the ethical principles that are outlined in the Declaration of Helsinki 2008, including, but not limited to:

- Institutional Review Board (IRB)/Independent Ethics Committee (IEC) review and favourable opinion/approval of study protocol and any subsequent amendments.
- Subject informed consent.
- Investigator reporting requirements.

Novartis will provide full details of the above procedures, either verbally, in writing, or both. Written informed consent must be obtained from each subject prior to participation in the study.

In approving the clinical protocol the IEC/IRB and, where required, the applicable regulatory agency are also approving the optional assessments e.g., [REDACTED] unless otherwise indicated. Where permitted by regulatory authorities, approval of the optional assessments can occur after approval is obtained for the rest of the study. If so, then the written approval will clearly indicate approval of the optional assessments is being deferred and the study, except for the optional assessments, can be initiated. When the optional assessments are not approved, then the approval for the rest of the study will clearly indicate this and therefore, the optional assessments will not be conducted.

10.3 Quality Control (Study Monitoring)

In accordance with applicable regulations, GCP, and Novartis procedures, Novartis personnel (or designated Clinical Research Organization [CRO]) will contact the site prior to the start of the study to review with the site staff the protocol, study requirements, and their responsibilities to satisfy regulatory, ethical, and Novartis requirements. When reviewing data collection procedures, the discussion will include identification, agreement and documentation of data items for which the CRF will serve as the source document.

The investigator and the head of the medical institution (where applicable) agrees to allow Novartis personnel or designated CRO direct access to all relevant documents and to allocate their time and the time to their staff to monitor to discuss findings and any issues.

Monitoring visits will be conducted in a manner to ensure that the:

- Data are authentic, accurate, and complete.
- Safety and rights of subjects are being protected.
- Study is conducted in accordance with the currently approved protocol and any other study agreements, GCP, and all applicable regulatory requirements.

The investigator and the head of the medical institution (where applicable) agrees to allow the monitor direct access to all relevant documents.

10.4 Quality Assurance

To ensure compliance with GCP and all applicable regulatory requirements, Novartis may conduct a quality assurance assessment and/or audit of the site records, and the regulatory agencies may conduct a regulatory inspection at any time during or after completion of the study. In the event of an assessment, audit or inspection, the investigator (and institution) must agree to grant the advisor(s), auditor(s) and inspector(s) direct access to all relevant documents and to allocate their time and the time of their staff to discuss the conduct of the study, any findings/relevant issues and to implement any corrective and/or preventative actions to address any findings/issues identified.

10.5 Study and Site Closure

The study will be close when it is completed, as defined in Section 3.1.

Upon completion or termination of the study, the Novartis personnel (or designated CRO) will conduct site closure activities with the investigator or site staff (as appropriate), in accordance with applicable regulations, GCP, and Novartis Standard Operating Procedures.

Novartis reserves the right to temporarily suspend or terminate the study at any time for reasons including (but not limited to) safety issues, ethical issues, or severe non-compliance. If Novartis determines that such action is required, Novartis will discuss the reasons for taking such action with the investigator or head of the medical institution (where applicable). When feasible, Novartis will provide advance notice to the investigator or head of the medical institution of the impending action.

If a study is suspended or terminated for **safety reasons**, Novartis will promptly inform all investigators, heads of the medical institutions (where applicable), and/or institutions conducting the study. Novartis will also promptly inform the relevant regulatory authorities of the suspension/termination along with the reasons for such action. Where required by applicable regulations, the investigator or head of the medical institution must inform the IRB/IEC promptly and provide the reason(s) for the suspension/termination.

10.6 Records Retention

Following closure of the study, the investigator or head of the medical institution (where applicable) must maintain all site study records (except for those required by local regulations to be maintained elsewhere) in a safe and secure location. The records must be easily accessible when needed (e.g., for a Novartis audit or regulatory inspection) and must be available for review in conjunction with assessment of the facility, supporting systems, and relevant site staff.

Where permitted by local laws/regulations or institutional policy, some or all of the records may be maintained in a format other than hard copy (e.g., microfiche, scanned, electronic); however, caution must be exercised before such action is taken. The investigator must ensure that all reproductions are legible and are a true and accurate copy of the original. In addition, they must meet accessibility and retrieval standards, including regeneration of a hard copy, if required. The investigator must also ensure that an acceptable back-up of the reproductions exists and that there is an acceptable quality control procedure in place for creating the reproductions.

Essential documents (written and electronic) should be retained for a period of not less than fifteen (15) years from the completion of the Clinical Trial unless the Sponsor provides written permission to dispose of them or, requires their retention for an additional period of time because of applicable laws, regulations and/or guidelines.

The investigator must notify Novartis of any changes in the archival arrangements, including, but not limited to archival of records at an off-site facility or transfer of ownership of the records in the event that the investigator is no longer associated with the site.

10.7 Provision of Study Results to Investigators, Posting of Information on Publicly Available Clinical Trials Registers and Publication

Where required by applicable regulatory requirements, an investigator signatory will be identified for the approval of the clinical study report. The investigator will be provided reasonable access to statistical tables, figures, and relevant reports and will have the opportunity to review the complete study results at a Novartis site or other mutually-agreeable location.

Novartis will also provide the investigator with the full summary of the study results. The investigator is encouraged to share the summary results with the study subjects, as appropriate.

12.2 Appendix 2: Cockcroft-Gault

The Cockcroft-Gault formula is a commonly-used surrogate marker for actual creatinine clearance and employs creatinine measurements and a subject's weight (kg) to predict the clearance [Cockcroft, 1976].

$\text{CrCl (mL/min)} = \frac{Q \times (140 - \text{age [years]}) \times \text{actual body weight (kg)}^a}{72 \times \text{serum creatinine (mg/dL)}}$
CrCL=creatinine clearance Q=0.85 for females Q=1.0 for males

OR

$\text{CrCl (mL/min)} = \frac{K \times (140 - \text{age [years]}) \times \text{actual body weight (kg)}}{\text{serum creatinine } (\mu\text{mol/L)}}$
K=1.04 for females K=1.23 for males

If the subject is obese (> 30% over ideal body weight), use ideal body weight in calculation of estimate CrCl.

a. Calculation of Ideal Body Weight Using the Devine Formula [Devine, 1974]

Male subjects:	50.0 kg + (2.3 kg x each inch over 5 feet) or 50.0 kg + (0.906 kg x each cm over 152.4 cm)
Female subjects:	45.5 kg + (2.3 kg x each inch over 5 feet) or 45.5 kg + (0.906 kg x each cm over 152.4 cm)

For example:

For a male subject with actual body weight = 90.0 kg, and height = 68 inches, the calculation would be as follows:

Ideal body weight= 50.0 + (2.3) (68-60) = 68.4 kg

This subject's actual body weight is >30% over ideal body weight. In this case, the subject's ideal body weight of 68.4 kg should be used in calculating estimated creatinine clearance.

References

Devine BJ. Case Number 25 Gentamicin Therapy: Clinical Pharmacy Case Studies. Drug Intelligence and Clinical Pharmacy. 1974; 8:650-655.

